9.5 Hypoglycemic Events

Hypoglycemia is only reportable as an adverse event when one of the following criteria is met:

- Severe Hypoglycemia: The event required assistance of another person due to altered consciousness, and required another person to actively administer carbohydrate, glucagon, or other resuscitative actions²¹. This means that the participant was impaired cognitively to the point that he/she was unable to treat himself/herself, was unable to verbalize his/her needs, was incoherent, disoriented, and/or combative, or experienced seizure or loss of consciousness. These episodes may be associated with sufficient neuroglycopenia to induce seizure or loss of consciousness. If plasma

glucose measurements are not available during such an event, neurological recovery attributable to the restoration of plasma glucose to normal is considered sufficient evidence that the event was induced by a low plasma glucose concentration.

- Hypoglycemia resulting in an SAE that may not otherwise meet the definition of Severe Hypoglycemia defined above.

When a hypoglycemic event meets the above reporting requirements, an Adverse Event Form should be completed. A severe hypoglycemia event should be considered a serious adverse event and follow the SAE reporting requirements.

9.6 Hyperglycemic/Ketotic Events

Hyperglycemia is only reportable as an adverse event when any of the following criteria is met:

- The event involved DKA, as defined by the Diabetes Control and Complications Trial (DCCT)²⁰, i.e. if all of the following are present:
 - Symptoms such as polyuria, polydipsia, nausea, or vomiting;
 - Serum ketones >1.5 mmol/L or large/moderate urine ketones;
 - Either arterial blood pH <7.30 or venous pH <7.24 or serum bicarbonate <15; and
 - Treatment provided in a health care facility
- Evaluation or treatment was obtained at a health care provider facility for an acute event involving hyperglycemia or ketosis, or the participant contacted the site and received guidance on how to manage the hyperglycemia/ketosis
- Prolonged hyperglycemia: defined as meter BG \geq 300 mg/dL for over 1 hour and ketones >1.0 mmol/L
- Hyperglycemia resulting in an SAE that may not otherwise meet the above criteria

When a hyperglycemia/ketotic event meets the above reporting requirements, Adverse Event Form should be completed.

Events meeting DKA criteria should be considered a serious adverse event and follow the SAE reporting requirements. Hyperglycemia events not meeting criteria for DKA generally will not be considered as serious adverse events unless one of the SAE criteria above is met

9.7 Relationship of Adverse Event to Devices or Study Procedures

The investigator will be responsible for deciding on the causal relationship of the AE. Specifically, the investigator will report whether the AE was related to study procedures and/or related to the devices (participant's own insulin pump, study CGM and Omnipod 5).

To ensure consistency of adverse event causality assessments, investigators should apply the following general guidelines when determining whether an adverse event is related.

The causal relationship to the study procedures and the devices for each adverse event will be rated as follows:

- Unrelated: The event is not related to the procedures or the investigational device.
- Possibly Related: The temporal sequence is such that the relationship is not unlikely or there is no contradicting evidence that can reasonably explain the participant's condition. There is a possibility of any relation between the event and the procedures or the devices.
- Related: The temporal sequence is relevant, or the event abates upon completion of the procedure/ use of devices, or the event cannot be reasonably explained by the participant's condition or comorbidities. The event is related or most likely associated with the procedures or the devices.

9.8 Severity (Intensity) of Adverse Events

The severity (intensity) of an adverse event will be rated on a three-point scale: (1) mild, (2) moderate, or (3) severe. A severity assessment is a clinical determination of the intensity of an event. Thus, a severe adverse event is not necessarily serious. For example, itching for several days may be rated as severe, but may not be clinically serious.

- Mild: Usually transient, requires no special treatment, and does not interfere with the participant's daily activities.
- Moderate: Usually causes a low level of inconvenience, discomfort or concern to the participant and may interfere with daily activities but is usually ameliorated by simple therapeutic measures and participant is able to continue in study.
- Severe: Interrupts a participant's usual daily activities, causes severe discomfort, may cause discontinuation of study device, and generally requires systemic drug therapy or other treatment.

9.9 Outcome of Adverse Events

The outcome of each reportable adverse event will be classified by the investigator as follows:

- Recovered/Resolved – The participant recovered from the AE/SAE without sequelae. Record the AE/SAE stop date.
- Recovered/Resolved with Sequelae – The event persisted and had stabilized without further anticipated change in the event status. Record the AE/SAE stop date.
- Fatal – A fatal outcome is defined as the SAE that resulted in death. Only the event that was the cause of death should be reported as fatal. AEs/SAEs that were ongoing at the time of death; however, were not the cause of death, will be recorded as “resolved” at the time of death.
- Not Recovered/Not Resolved (Ongoing) – An ongoing AE/SAE is defined as the event was ongoing with an undetermined outcome.
 - An ongoing outcome will require follow-up by the site in order to determine the final outcome of the AE/SAE or until participant completes the study.
 - The outcome of an ongoing event at the time of death that was not the cause of death, will be updated and recorded as “resolved” with the date of death recorded as the stop date.

- Unknown – An unknown outcome is defined as an inability to access the participant or the participant's records to determine the outcome (for example, a participant that was lost to follow-up).

If any USADEs are ongoing when a participant completes the study (or withdraws), the participant will continue to be followed until the event resolves or has no prospect of improvement or change, even after the participant has completed all applicable study visits/contacts, unless that participant has withdrawn their consent. For all other reportable adverse events, data collection will end at the time the participant completes the study. Note: Participants should continue to receive appropriate medical care for an adverse event after their participation in the study ends.

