9 SAFETY

9.1 Types of Known Risks and Benefits

There are known risks and benefits. Most of the risks are not unique to the study and are typical for patients using insulin pumps, CGM, and BG meters. For the Control group, the applicable Instructions for use (IFU) should be referenced for any additional potential risks.

The known risks are as follows:

- Hypoglycemia and/or hyperglycemia as a result of change in diet, activity, diabetes management or insulin regimen during the study.
- Hypoglycemia and/or hyperglycemia as a result of over or under delivery of insulin due to a device defect, failure or malfunction of any of the system components.
- Hypoglycemia, hyperglycemia, diabetic ketoacidosis, seizure, coma or death related to insulin administration, pump use or misuse, or Omnipod 5 System use or misuse.
- Use of the Pod – because the Pod uses only rapid-acting insulin, users are at increased risk for developing hyperglycemia if insulin delivery is interrupted. If it is untreated, prolonged hyperglycemia can lead to diabetic ketoacidosis (DKA). DKA can cause symptoms such as breathing difficulties, shock, coma, or death. Further, occlusions can interrupt insulin delivery and lead to hyperglycemia or DKA. Other potential risks associated with using the Pod are:
 - Anaphylaxis (allergic shock)
 - Bruising at the Pod site
 - Bleeding at the Pod site
 - Erythema (redness at the Pod site)
 - Excoriation (raw skin at Pod site)
 - Pruritus (itching)
 - Induration (hardening of the skin at the Pod site)
 - Infection (can include heat, redness, swelling, pain, and drainage)
 - Inflammation (redness, swelling)
 - Skin reaction to adhesive at the Pod site
 - Papule (small, solid raised area on the skin similar to a pimple)
 - Pain or discomfort
 - Ulceration (skin sores)
 - Vesicles (blisters)
- Use of the CGM – risk of bruising, infection, pain and/or bleeding at the site of insertion, and skin site reaction to adhesive

- Use of the Controller – risk of overheating of the Omnipod 5 Controller charging port and cable, including the cable melting, deforming, or discoloring. The excess heat may cause minor burns if those areas of the controller are touched or could lead to fire.
- On rare occasions, the CGM sensor may break and leave a small portion of the sensor under the skin that may cause redness, swelling, or pain at the insertion site, and may require surgical removal.

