9.3 Adverse Events

Adverse Event (AE): is defined as any untoward medical occurrence, unintended disease or injury, or any untoward clinical signs (including an abnormal laboratory finding) in participants, users or other persons, whether or not related to the investigational medical device.

NOTE 1: This includes events related to the investigational medical device or the comparator.²²

NOTE 2: This definition includes events related to the procedures involved (any procedure in the clinical investigation plan).²²

Serious Adverse Event (SAE): Any untoward medical occurrence that:

- Led to death
- Led to serious deterioration in the health of the participant, that either resulted in:

- a life-threatening illness or injury, or
 - a permanent impairment of a body structure or a body function, or
 - hospitalization, or prolonged existing hospitalization, or
 - medical or surgical intervention to prevent life-threatening illness or injury or permanent impairment to a body structure or a body function.
- Led to fetal distress, fetal death, or a congenital abnormality or birth defect.

NOTE: Planned hospitalization for a pre-existing condition, or a procedure required by the clinical investigational plan, without serious deterioration in health, is not considered a serious adverse event.²²

Unanticipated Serious Adverse Device Effect (USADE): Any serious adverse effect on health or safety or any life-threatening problem or death caused by, or associated with, a device, if that effect, problem, or death was not previously identified in nature, severity, or degree of incidence in the investigational plan or application (including a supplementary plan or application), or any other unanticipated serious problem associated with a device that relates to the rights, safety, or welfare of participants.²²

Adverse Device Effect (ADE): An adverse device effect (ADE) is an adverse event related to the use of an investigational medical device.²²

NOTE 1: This definition includes any adverse event resulting from insufficient or inadequate instructions for use, deployment, implantation, installation, or operation, or any malfunction of the investigational medical device.²²

NOTE 2: This definition includes any event resulting from user error or from intentional misuse of the investigational medical device.²²

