9.4 Reportable Adverse Events

Adverse events will be assessed on an ongoing basis throughout the study. Adverse event reporting will begin at the start time of the standard therapy (i.e., insertion of the CGM sensor) and continue until the participant's participation has ended. All adverse events must be followed until resolution, or until the AE has stabilized, or until the study has been completed.

Pre-existing medical conditions or symptoms observed prior to the start time of the standard therapy phase will not be recorded as an AE and should be collected in the participant's medical history. In the event there is a change (i.e., worsening) in the pre-existing medical condition or symptoms after enrollment meeting the criteria of a reportable adverse event, then an AE must be reported.

For this protocol, a reportable adverse event includes any untoward medical occurrence that meets one of the following criteria:

1. An SAE
2. An ADE unless excluded from reporting in Hypoglycemic Events and Hyperglycemic/Ketotic Events sections below
3. An AE not related to a study device issue which leads to temporary or permanent discontinuation of the study devices or the participant's own insulin pump, or creates a clinically significant impact on a participant's glucose control
4. An AE that affects the participant's ability to complete any study procedures
5. An AE for which a visit is made to a hospital emergency department
6. Hypoglycemic Events as defined below
7. Hyperglycemia/Ketotic Events as defined

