10 STOPPING CRITERIA

10.1 Participant Discontinuation of Study Participation

In the case of a USADE for Intervention group participants, the Medical Monitor will determine if the use of the investigational device will be suspended while the problem is diagnosed. The use of the investigational device may continue if the Medical Monitor believes the event is explainable, unlikely to reoccur and that it is safe for the participant to continue using the device. Alternatively, the Medical Monitor may request the study participant, or all study participants, to stop using the investigational device or to only use in Manual Mode. Should Intervention group study participants be required to stop using the study device or to only use in Manual Mode due an USADE, use of the study device or Automated Mode will not be restarted until approval is received from the regulatory authorities.

Use of the investigational device by a participant will be discontinued if any of the following occur:

- The investigator, sponsor, or Medical Monitor believes it is unsafe for the participant to continue in the study for any reason. This could be due to the development of a new medical condition or worsening of an existing condition; or participant behavior contrary to the indications for use of the device that imposes on the participant's safety.
- The participant requests that the treatment be stopped
- Participant pregnancy
- Two distinct episodes of DKA as defined above
- Two distinct severe hypoglycemia events as defined above
- One episode of DKA and one severe hypoglycemia event as defined above

An additional requirement for continued study device use following a single DKA or severe hypoglycemia event will be that (1) the site investigator believes that the event is explainable, unlikely to recur, and that it is safe for the participant to continue to use the system and (2) the Medical Monitor concurs. If the Medical Monitor determines that the occurrence of the event indicates that it is not safe for the participant to continue to use the system, use will be discontinued, and the participant will be withdrawn from the study.

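### Under Protocol 9.9, a serious adverse event that is not a USADE and is still ongoing when the participant leaves has no assured final outcome

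*Protocol*

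**What the plan says.** Protocol 9.9 sets two rules for an event unresolved at exit. For USADEs: "If any USADEs are ongoing when a participant completes the study (or withdraws), the participant will continue to be followed until the event resolves". That follow-up stops sooner only where no further change is expected or consent has been withdrawn. For everything else: "For all other reportable adverse events, data collection will end at the time the participant completes the study". While the participant is still in the study, 9.9 covers all ongoing events: "An ongoing outcome will require follow-up by the site in order to determine the final outcome of the AE/SAE", with the participant's completion as the alternative end point.

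Protocol 9.4 states a general rule: "All adverse events must be followed until resolution, or until the AE has stabilized, or until the study has been completed". The same section says that AE reporting will "continue until the participant's participation has ended", and 7.9 ends participation at withdrawal.

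A USADE, as defined in 9.3, is an effect that "was not previously identified in nature, severity, or degree of incidence in the investigational plan" or application. Protocol 9.1 names these among the known risks: "Hypoglycemia, hyperglycemia, diabetic ketoacidosis, seizure, coma or death related to insulin administration", pump use or Omnipod 5 use. Sections 9.5 and 9.6 make severe hypoglycemia and DKA serious adverse events.

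Under 10.1, if the Medical Monitor decides after a single DKA or severe hypoglycemia event that going on with the system is not safe, "use will be discontinued, and the participant will be withdrawn from the study".

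**The concern.** Post-exit follow-up in 9.9 depends on whether an event was an unanticipated device effect, not on how serious it was. The serious events one most expects in this population are known risks of insulin delivery, so they normally fall on the side where collection stops. The same holds for serious events with no device relationship.

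At stake is the outcome field for those events. Both documents require each reportable event to be given an outcome, including fatal and resolved with sequelae (Protocol 9.9, SAP 6.4), and both call for a separate listing of events leading to death (Protocol 12.3.1, SAP 6.5). A serious event open at the last contact would be reported as Not Recovered/Not Resolved (Ongoing). A later death or lasting harm might never reach the database.

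**Working it through.** No figure in the plan bears on this point and no arithmetic applies. The check is a comparison of the passages.

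1. **Which rule applies to DKA and severe hypoglycemia?** Both are SAEs (9.5, 9.6). Both are known risks in nature (9.1), so they ordinarily fail the USADE definition in 9.3. They are then among the other reportable events in 9.9. An exception is possible: 10.3 has the Medical Monitor adjudicate whether such an event is unanticipated, and one that then met the USADE definition would be followed.

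2. **What happens before exit?** The site follows every ongoing event towards a final outcome (9.9). An event that resolves or stabilizes by the last visit therefore has its outcome recorded. Only an event still open at exit is exposed.

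3. **What happens at completion?** For a non-USADE, 9.9 is explicit: data collection stops.

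4. **What happens at withdrawal?** The USADE sentence names both completion and withdrawal. The sentence for other events names completion only, so 9.9 is silent. Section 7.9 ends participation at withdrawal and 9.4 ends AE reporting with participation. Together they suggest that collection stops, but that is an inference.

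5. **Does 9.4 settle it?** Its end point is completion of the study, without saying whose.
   - If it means the trial, 9.4 requires follow-up past the participant's exit and conflicts with 9.9.
   - If it means the participant's own exit, 9.4 agrees with 9.9 and the gap stands.

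   A site cannot tell from the text which is intended.

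6. **Can the event that ends participation be the one affected?** Yes, by one stated route: the single-event branch of 10.1, if the event is still open at the Early Withdrawal visit. The criteria based on two events (two DKA, two severe hypoglycemia, or one of each) stop use of the investigational device; 10.1 does not state withdrawal from the study for them.

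7. **Which analyses depend on the outcome after exit?** Severe hypoglycemia and DKA are analyzed as event counts, participants with at least one event, and rates per 100 person-years (Protocol 12.3.3, SAP 5.2.5). AE tables are by phase, category, seriousness, severity and relationship (Protocol 12.3.1, SAP 6.5). None uses the outcome reached after exit. The efficacy endpoints do not use it either. What depends on it is the outcome classification and the listing of events leading to death.

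**The case against.** The strongest defense is that existing provisions already catch most of these outcomes. Ongoing events are followed until exit. The Early Withdrawal visit is an office visit that includes an AE assessment (7.9, Table 1). Section 9.11 calls for the discharge summary whenever an SAE involves hospitalization, and for every effort to obtain a death certificate; neither is limited to USADEs. DKA, as defined in 9.6, involves treatment in a health care facility, so records will exist. An event still open is reported openly as ongoing. Limiting follow-up after exit is also a deliberate choice, and the Safety Management Plan, which is not available here, may add to it.

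Most of this stands, and it is why the point is small. It does not close the gap. The withdrawal visit records status on that day. A discharge summary exists only if the participant was hospitalized, which the severe hypoglycemia definition in 9.5 does not require, and it may not show later sequelae. The death-certificate provision helps only if the site learns of the death.

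A reader might infer more than the text supports:

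- That outcomes of DKA and severe hypoglycemia are not collected at all. They are, for every event that resolves or stabilizes by exit.
- That 9.9 generally cuts off the events that end participation. Withdrawal is stated only for the single-event branch of 10.1, and the event must also be unresolved at the withdrawal visit.
- That the safety comparison is weakened. The counts and rates on which it rests do not change.

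**Conclusion.** The point holds in a limited form. A serious event that is not a USADE and is still ongoing at exit has no assured final outcome under 9.9, and 9.4 and 7.9 do not resolve the matter. This rests on the ordinary reading that DKA and severe hypoglycemia are anticipated because 9.1 lists them and, for withdrawn participants, on the inference that collection ends when participation does.

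The consequence is incomplete outcome data for such events, possibly including a later death or sequela. The number affected is likely very small. The documents give neither an expected count of serious events nor their duration at exit, so it cannot be estimated. The primary endpoint, the secondary endpoints, and the counts and rates of severe hypoglycemia and DKA are not affected. The change is worth making because it is cheap and concerns the most serious events, not because a conclusion of the trial is at risk.

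**What to change.** In Protocol 9.9, extend the existing USADE follow-up sentence to every SAE ongoing at completion or withdrawal: outcome data are collected until the event is resolved or stable, unless consent is withdrawn. State in 9.9 that the rule for the remaining non-serious events applies at withdrawal as well as at completion. In 9.4, say whether the end point is the trial or the participant's exit, and use the same SAE wording. In 7.9, add that the end of participation does not end outcome collection for an open SAE. These changes concern data collection only and leave the discontinuation rules in 10.1 untouched.

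One consequential edit is needed in SAP 5.2.5. For a withdrawn participant, the last AE date can set the end of the randomized period when person-time is calculated. The SAP should say that an outcome date obtained after exit does not count for this purpose, so that longer follow-up of an event does not lengthen the denominator of its rate.

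The cost is a protocol wording change, a few telephone calls or record requests, and a few AE forms that stay open after the last visit.
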